
POPULATION
	
Our population includes newly married women, pregnant women, and mothers with young children aged 6 months or younger located in two subdistricts of Gazipur district in Bangladesh. According to the Demography and Health Surveys of 2014, women in Bangladesh tend to marry early. By age 18, 50% are married and their first child arrives 1.5 years later, which means that many women become mothers as teens. Moreover, 98.6% get married and nearly all have at least one child. As a result, there is virtually no selection into fertility in this setting. Two thirds of women deliver their child at home, have between one and two antenatal visits. Half have primary education or less, and less than 35% work outside home (half of which are employed in agriculture). Husbands are on average 10 years older, have similar levels of education, and the vast majority work in agriculture or in the informal sector. Moreover, Bangladesh has one of the highest rates of malnutrition in the world. 20% of children born in the country every year are born either “small” or “very small” (Demography and Health Survey, DHS 2014), 41% of those below the age of 5 are stunted, and about five million children are out of school (World Bank, 2015).

SELECTION AND ENROLMENT
	
Eligibility criteria for inclusion:
 
 1. Listed in the digital database of Kapasia Model 2. Permanent residence of any of the two subdistricts of Gazipur district in Bangladesh 3. Newly married women 4. Pregnant women 5. Mothers with young children aged 6 months or younger 
To be eligible, women must fulfill the first and the second criteria, any of the criteria from 3 to 5 must be fulfilled.

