4. AIMS / OBJECTIVES / HYPOTHESES

Our goal is to address three types of adversities that hinder women’s empowerment and early child development in low- and middle-income countries: low take-up of healthcare and other social safety net programs (including cash- and food-transfers), lack of knowledge about the importance of the early years on future child development and long-run outcomes, and psychological constraints associated with maternal depression. We aim to test to what extent these three interventions offer practical opportunities to improve maternal health, birth, and child development outcomes in cost-effective ways. We believe that these interventions might be even more effective than previous similar interventions because we will be targeting women

early in pregnancy (and in some cases even prior to conception), which is considerably earlier than most previous studies aimed at improving maternal and child outcomes.

Our specific **objectives** are:

- 1) Explore what are pregnant women’s views about the idea of a “healthy pregnancy” and how these perceptions translate to actual health behaviours and investments in children.
- 2) Investigate if providing the three following targeted interventions to women early in pregnancy offers cost-effective ways to enhance maternal wellbeing and children’s physical and mental development:
 - a. Information about women’s eligibility to health services and other safety net programs and assist them with the enrolment process.
 - b. Information to pregnant mothers and their families on the importance of the early-life environment, and especially the 9-month in utero period, in laying the foundations for a child’s lifelong success.
 - c. Psychological counselling to pregnant women starting early in pregnancy.

Our study has four main **hypotheses**, each of which will be tested by a different intervention:

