	ভাত	২ বাটি (২৫০ মি.লি.+২৫০ মি.লি.)
	মন ডাল	১ বাটি (২৫০ মি.লি.)
	শাক-সবজি	১½ বাটি (২৫০ মি.লি.+১২৫ মি.লি.)
	মাছ/মাংস/ডিম	১ টুকরা (মাঝারি)

Figure 3 Five-meal menu for pregnant woman (Bengali).

can protect a child against low birth weight and stunting (short height) in infancy, and psychological problems, and diabetes or hypertension in adulthood. In contrast, children of mothers who suffer from long periods of stress during pregnancy can develop future health problems when they become adults themselves. Therefore, taking nutritious food regularly, managing stress, and thinking positively from the earliest stages of pregnancy are important for the child in the near- as well as in the long-term. It’s never too early to incorporate these positive changes to your routine.”

The third intervention involves offering psychological counselling based on Cognitive Behavioural Therapy, which will be provided by trained counsellors from Moner Bondhu (<https://www.monerbondhu.org/>). The content will follow the WHO-adopted and evidence-based programme called Thinking Healthy, specifically focusing on only the early (pre-delivery) sessions. Thinking Healthy has already been translated and adapted to Bengali (with the full manual for the management of perinatal depression available for free from the WHO website here: <https://apps.who.int/iris/bitstream/handle/10665/152936/WHO-MSD-MER-15.1-ben.pdf?ua=1&ua=1>). Eligible and willing participants who would be randomly assigned to receive this treatment will be contacted by an officer from Moner Bondhu. Participants will be invited to take part in 4 group counselling sessions, each lasting approximately 1-1.5 hours. The group will consist of other pregnant women from the same village enrolled in this study. We anticipate the groups will be approximately 22 women or less. Counsellors from Moner Bondhu will identify an appropriate venue with comfortable furnishing and privacy to hold the sessions. The sessions will use narratives, or stories, to engage women and then open the floor to discussion on the issues of (1) mother’s physical health, (2) coping with stress, (3) and mother’s relationship with the people around her. They will be modelled after the THPP

intervention (specifically see Chapter 2 in the THPP Manual). However, we will adapt the sessions to include a focus on identifying and coping with stressors.

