To evaluate the impact of these three interventions, we will conduct a 3x2 factorial RCT across two sub-districts in rural Bangladesh. The two information treatments will be cross randomized with the one mental health intervention. The mental health intervention will be randomized at the Union Health and Family Welfare Centre (UHFWC) level (there are 20 total UHFWCs across the 2 Upazilas), stratified by sub-district, and allocated at a 1:1 ratio. We will then randomly select 120 villages within subdistricts, stratified by UHFWC, to participate. The information interventions will be randomized at the village level, stratified by UHFWC, with 40 villages receiving information and enrolment support for government programs, 40 villages receiving additional information on the importance of early life conditions, and 40 control (no information) villages. Eligible participants will be pregnant women and mothers with young children aged 6 months or younger. We will aim to recruit 22 women per village to be part of the study sample.

We will use two types of data, (i) the data from the digital information system of Kapsasia Model built at the sub-district level by the local government, which we call *administrative data*, and (ii) household and individual survey data including elicitation of maternal beliefs of prospective and existing mothers that we will collect as a part of the study, which we call *household survey data*. This survey will be conducted on the sample of 22 women per village for a **total sample of 2,640 women**. The administrative data include information (e.g., age, education, occupation, mobile phone number, pregnancy status, birth outcomes, number of children) on *all* registered newly married couples in our study area, including the 22 women per village in our study sample, and will identify key outcomes such as pregnancy status and birth outcomes. We will conduct a baseline survey with an endline 10 months later, and we plan to conduct a midline survey by phone (which will likely be funded using internal funds² from the University of Sydney and University of Melbourne) to measure parental inputs in the in utero period. The schedule of enrolment, intervention and evaluations is given in Figure 1.

² They have not been mentioned in the budget as no firm commitment has been received yet.

The study schedule	Study period													
	Baseline							Midline				Endline		

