	1st month	2nd month	3rd month	4th month	5th month	6th month	7th month	8th month	9th month	10th month	11th month	12th month	13th month	14th month
Enrolment														
Eligibility Screening	X													
Consent collections		X												
Randomization & allocation to treatments and control group			X											
Interventions/ Treatments														
1. Information and enrolment support to govt. programs				X	X	X	X	X	X	X	X			
2. 1 + Information on the importance of early life conditions				X	X	X	X	X	X	X	X			
3. Psychological counselling				X	X	X	X	X	X	X	X			
Evaluations														
Compliance Check - if individuals and groups assigned to treatments and controls are in fact complying to the assignment					X	X	X	X	X	X	X			
Household characteristics and other basic information, houses, lands, and asset ownership, economic activities and employment, beliefs, women mental health, preferences		X										X		
Parents time and monetary investment on children								X						
Anthropometry & health, children’s mental health and development, take up of health care services, participation in social transfers/safety net programs, parenting style, parents time and monetary investment on children, food intake/share, food insecurity & non-food expenditures, women empowerment, intimate partner violence													X	
Data Analysis														X X
Report Writing/ Publication														X X

Figure – 1: Schedule of enrolment, intervention, and evaluations

Power Calculation: Given the sample sizes above and accounting for the varied clustered design, we would be powered to detect a Minimum Detectable Effect (MDE) size of 0.31 of a standard deviation (SD) change for the mental health intervention (randomized at the Health Centre (UHFWC) level with the conservative estimate of 20 centers). For the information arms, we would be powered to detect a 0.19SD change for either of the information interventions (main effects only). As benchmark for the MDEs on mental health interventions, Rahman et al. (2008) found that a mental health intervention similar to the one proposed here improved mothers’ mental health by 0.70SD, while Sikander et al. (2019) found that a more scalable, peer-delivered version of the intervention increased mothers’ mental health by 0.30SD. A tele-counseling intervention in Bangladesh improved mental health by 0.65SD (Vlassopolous et al. (2021)).

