11. TIMELINES / MILESTONES

An approximate study timeline is provided in Figure 2. We plan to complete the study within 14 months from start. In the first month, the eligibility criteria of participants which will be selected from the Kapasia Model digital database, will be re-checked, and informed consents of the eligible participants will be sought. This will be followed by commencement of the baseline survey in the second month of the study, and the random allocation of participants to different treatments will be achieved in the third month. The list of participants that will receive psychological counselling will be given to the relevant implementing partner Moner Bondu,

and the rest of interventions will be carried out by the research team. In the fifth month, compliance to treatments and control status will be checked followed by a midline telephone survey in the eighth month. We will conduct the endline survey after 10 months of the intervention followed by data analysis and report writing / manuscript preparation.

[figure not shown]

Figure 2: Study Timeline

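### The eligibility text, the counselling group and Figure 1 do not agree on which enrolled women can receive pre-delivery counselling, or when

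*Protocol*

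**What the plan says.** **Content and dose (Protocol, Section 6).** The counselling follows Thinking Healthy, "specifically focusing on only the early (pre-delivery) sessions". The dose is stated as: "Participants will be invited to take part in 4 group counselling sessions, each lasting approximately 1-1.5 hours". No interval between sessions is given.

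**Who attends (Section 6).** "The group will consist of other pregnant women from the same village enrolled in this study". Groups are expected to number about 22 women or fewer.

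**Intended timing (Section 4).** The objective is "Psychological counselling to pregnant women starting early in pregnancy". Hypothesis 3 attributes the lack of benefit to children in earlier programmes to a start in the third trimester.

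**Who is enrolled.** Section 6: "Eligible participants will be pregnant women and mothers with young children aged 6 months or younger". Section 2 is wider: "Our population includes newly married women, pregnant women, and mothers with young children aged 6 months or younger". Neither sets a gestational limit.

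**How counselling is allocated (Section 6).** By Union Health and Family Welfare Centre, 20 centres at 1:1, so an enrolled woman's assignment follows from her centre and not from whether she is pregnant.

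**Calendar.** Figure 1 puts screening in month 1 and consent in month 2. Section 11 states that "the random allocation of participants to different treatments will be achieved in the third month". The row "3. Psychological counselling" is marked in every month from 4 to 11, the same eight months as the two information rows.

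**The concern.** The counselling factor exists to test whether an early prenatal start helps mothers and children where later starts did not help children. That needs the women counted in the arm to be women who could have had the sessions before delivery. As written, the eligible population, the counselling group and the calendar each describe a different set of women.

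If women who cannot receive a pre-delivery session are analysed in the counselling arm, the average effect shrinks towards zero. A null result could then mean either that early counselling does not work or that it did not reach enough women in time. The secondary outcomes make this sharper. Birth weight is one of them, and for a mother enrolled with an infant it was fixed before allocation.

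**Working it through.** The protocol gives no completion rate, session spacing or gestation mix, so there is no planned figure to reproduce. The check has two parts.

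**Part 1: what follows from the text and a 9-month pregnancy**

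1. Mothers of infants up to 6 months are eligible under Sections 2 and 6. They have already delivered, so the number of pre-delivery sessions they can receive for that birth is zero, whatever the spacing.
2. Screening is in month 1 and counselling starts in month 4, a gap of 3 months. A woman who delivers in that gap also receives none.
3. A woman pregnant at month-1 screening delivers by about month 1 + 9 = month 10. Months 10 to 11 of the counselling row therefore fall essentially after every pregnancy present at screening.
4. Newly married women who conceive after enrolment could still be pregnant late in the window. They are eligible under Section 2 but are left out of the eligibility sentence in Section 6.

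**Part 2: how large the share could be (assumptions, not in the protocol)**

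Assume a 9-month pregnancy and gestation at screening uniform from *a* to *b* months. Let *t* be months since screening, so month 4 is t = 3 and month 11 is t = 10. The share of women pregnant at screening who have delivered by *t* is

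(b − (9 − t)) / (b − a), held between 0 and 1.

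| Point in the course | Gestation 0–3 | 0–6 | 0–9 | 2–9 |
|---|---|---|---|---|
| Session 1 in month 4, t = 3 | 0% | 0% | 3/9 = 33% | 3/7 = 43% |
| Session 4, weekly from month 4, t = 3.7 | 0% | 0.7/6 = 12% | 3.7/9 = 41% | 3.7/7 = 53% |
| Session 4, monthly in months 4–7, t = 6 | 0% | 3/6 = 50% | 6/9 = 67% | 6/7 = 86% |
| Session 4, course spread over months 4–11, t = 10 | 100% | 100% | 100% | 100% |
| Session 4, weekly, village starts staggered over the window | 40% | 63% | 75% | 88% |

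The last row averages the formula over session-4 times uniform from t = 3.7 to t = 10. For gestation 0–9 this is [(9² − 3.7²)/(2 × 9) + 1] / 6.3 = (3.74 + 1) / 6.3 = 75%.

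Taking the gestation mix at allocation in month 3 instead, session 1 is at t = 1. For gestation 0–9 the shares are 1.7/9 = 19% (weekly), 4/9 = 44% (monthly) and 8/9 = 89% (spread). Over all mixes the range still runs from 0% (0–3, weekly) to 100% (2–9, spread).

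**Dilution, for illustration only.** Suppose the Section 6 population is enrolled in proportion to time, 9 months of pregnancy and 6 of infancy. Then 6/15 = 40% of women have already delivered when enrolled. If they gain nothing from counselling, an average effect equal to the plan's minimum detectable 0.31 SD needs 0.31/0.60 = 0.52 SD among the rest. The protocol states no such mix.

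**The case against.** Figure 1 is a study-level calendar. It shows the months in which counselling is active somewhere in the trial and gives no schedule for a woman or a village. A reader might infer that Section 6 and Figure 1 state different doses. They do not: Figure 1 states no dose, and four sessions fit easily into eight months.

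A reader might also infer that most women allocated to counselling would deliver before completing the course. That cannot be derived. With weekly sessions from month 4 and gestation of 0–9 months at screening, 100% − 41% = 59% of women pregnant at screening are still pregnant at session 4. The 100% result needs each woman's sessions spread over the whole window, which the protocol nowhere says. Adding mothers in the proportion assumed above would leave 0.60 × 59% = 35% of allocated women still pregnant at session 4. That figure rests on an invented mix with no newly married women in it, and it sits uneasily with the aim of reaching women early. Part of the loss also comes from the three-month gap after screening and not from the length of the window.

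Nor does the group size conflict with the group definition. Groups of about 22 or fewer leave room for a subset of pregnant women among the 22 enrolled in a village.

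Finally, pre-delivery describes the session content and is not a rule for women who deliver mid-course, and a session calendar may properly sit in a manual or the analysis plan. All of this stands. It does not remove the disagreement on who is covered: Section 6 puts pregnant women in the groups, enrols mothers who have delivered, and allocates by centre. Newly married women may explain the late months of the window, but Section 6 leaves them out of its eligibility sentence.

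**Conclusion.** The point holds as an inconsistency on who can receive counselling and when. Three statements rest on the text and a 9-month pregnancy alone. Enrolled mothers of infants can have no pre-delivery session for that birth. Neither can women who deliver between screening and month 4. For women pregnant at screening, months 10 to 11 come essentially too late.

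The number of women affected is unknown. Under the assumptions shown, the share of women pregnant at screening who deliver before session 4 runs from 0% to 100%, so neither a majority nor a small minority can be claimed. The consequence is that the arm testing hypothesis 3 mixes women who can and cannot receive the prenatal intervention. This dilutes the effect by an amount the plan does not fix and leaves a null result hard to interpret. It should be corrected.

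**What to change.** 1. Reconcile the eligibility text in Sections 2 and 6, the description of the counselling group in Section 6 and the counselling row of Figure 1. They should agree on which enrolled women are offered counselling and on its timing relative to delivery. The number, spacing and timing of sessions are for the sponsor to decide.
2. Keep the intention-to-treat comparison by centre as the main analysis.
3. In the compliance check already marked for months 5 to 11, record sessions attended before delivery. Attendance can come from the 50 Taka payment per group meeting (Section 10) and delivery from the birth information in the administrative data (Section 6). The sponsor should confirm that these data hold the delivery date. This count arises after allocation, so it describes what was delivered and does not define a comparison group.
4. Also report the counselling effect by pregnancy status at allocation, classified in the same way in both arms. That status is fixed before treatment, so the comparison stays randomised.

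The cost is protocol wording and a minor extra analysis.

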	
Child outcomes: Health at birth (birth weight and low birth weight); Developmental outcomes (Bayley Scales of Infant and Toddler Development that captures children’s cognitive, language, motor, adaptive); Health (weight-for-length, length-for-age, acute respiratory illnesses); Stress (Biomarkers of stress from hair samples).

STUDY DURATION	
The estimated time (in months) from when the study opens to enrolment until completion of data analyses is 14 months.

INTERVENTION/S	
We will provide three interventions through the Kapasia Model of Maternal and Child Health (henceforth, Kapasia Model):
 
 1) Information about women’s eligibility to health services and other safety net programs (cash transfers, food transfers) offered by the government, and assist them with the enrolment process. 2) Information to pregnant mothers and their families on the importance of the early-life environment, and especially the 9-month in utero period, in laying the foundations for a child’s lifelong success. 3) Psychological counselling to pregnant women starting early in pregnancy.
NUMBER OF PARTICIPANTS	
A total of 2,640 women from 120 villages (22 women per village) from two sub-districts of Gazipur district will take part in this study. The information interventions will be randomized at the village level, with 40 villages receiving information and enrolment support for government programs, 40 villages receiving additional information on the importance of early life conditions, and 40 control (no information) villages. The psychological counselling intervention will be randomized at the Union Health and Family Welfare Centre (UHFWC) level (there are 20 total UHFWCs across the 2 subdistricts), stratified by sub-district, and allocated at a 1:1 ratio.

accurately reflect chronic hormone secretion (see Baranov et al. 2022 for a discussion and an example of successful hair cortisol measurement with mother and child dyads in Pakistan). Hair sample collection was funded with this proposal, and further funding will be sought for laboratory extraction of analysis. Hair samples are easily storable and stable for 1-2 years.

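### The protocol does not reconcile who is assigned to counselling with who is offered it, and the 0.31 SD detectable effect makes no allowance for assigned women outside the pregnant-only groups

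*Protocol*

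**What the plan says.** **Assignment.** Protocol Section 6: "The mental health intervention will be randomized at the Union Health and Family Welfare Centre (UHFWC) level", "stratified by sub-district, and allocated at a 1:1 ratio". With 20 centres, this assigns every enrolled woman served by a counselling centre. The Synopsis gives the sample: "A total of 2,640 women from 120 villages (22 women per village").

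**Who is enrolled.** Section 6: "Eligible participants will be pregnant women and mothers with young children aged 6 months or younger". The Synopsis (Population) is wider: "Our population includes newly married women, pregnant women, and mothers with young children aged 6 months or younger". Its selection rule requires only one of these three conditions, besides listing in the database and residence.

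**Who is offered counselling.** Section 6 says that women assigned to counselling will be contacted and invited to four group sessions. It then describes the groups: "The group will consist of other pregnant women from the same village enrolled in this study". The content follows an existing programme, "specifically focusing on only the early (pre-delivery) sessions". On size: "We anticipate the groups will be approximately 22 women or less". Section 4 likewise describes the intervention as counselling of pregnant women.

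**Timing.** Section 11 puts allocation in month 3 and has a list of the women to be counselled handed to the implementing partner. Figure 1 runs counselling over months 4 to 11.

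**Outcomes and power.** Maternal depression, anxiety, stress and intimate partner violence are among the primary outcomes (Section 9). The power paragraph in Section 6 gives a detectable effect of 0.31 SD for counselling on the full sample. It cites benchmark effects of 0.30, 0.65 and 0.70 SD.

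**The concern.** Eligibility lets in women who are not pregnant, and centre-level randomisation assigns all of them. The group description covers only pregnant women. The protocol sets no recruitment quota by pregnancy status and does not say what an assigned woman who is not pregnant receives.

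The maternal primary outcomes can be measured in every enrolled woman, whatever her pregnancy status. If assigned women outside the groups are analysed as counselled, the comparison averages women who were offered counselling with women who were not. A null result could then be read as a failure of counselling when part of the arm was never within its delivery rule. The power statement shows no allowance for this.

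**Working it through.** **1. Inputs.** From the protocol: 120 × 22 = 2,640 women; 20 centres, so 2,640 / 20 = 132 women per centre on average; detectable effects of 0.31 SD (counselling) and 0.19 SD (information); benchmarks of 0.30, 0.65 and 0.70 SD. Not stated, hence assumed: two-sided alpha 0.05, 80% power, no dropout, and the ICC.

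**2. The plan's own figure.** Detectable effect = (critical value + power quantile) × √[(4/K) × (ICC + (1 − ICC)/m)].

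- Counselling, K = 20, m = 132, ICC = 0.05: √[0.2 × (0.05 + 0.95/132)] = 0.107. With normal quantiles, 2.80 × 0.107 = 0.300; with t on 18 df, 0.317. Exactly 0.31 needs an ICC of 0.0475 (t) to 0.054 (normal).
- Information arm against control, K = 80, m = 22, ICC = 0.05: 0.191 (normal) or 0.194 (t), against the stated 0.19.

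The figure cannot be strictly reproduced, because its inputs are not given. Both stated values do fit an ICC near 0.05 with all 132 women per centre and no dilution.

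**3. Dilution.** Let p be the share of assigned women who are offered counselling, and suppose the others have no effect. Then the effect over all assigned women = p × effect in women offered it, and the effect needed in those women = 0.31 / p. Power uses the standard error implied by 0.31, which is 0.31 / 2.80 = 0.111. The last column limits the comparison to the share p of women in both kinds of centre, so m = 132p, with ICC 0.0475 and t on 18 df.

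| p (assumed) | Effect needed, SD | 0.30 becomes (power) | 0.65 becomes (power) | 0.70 becomes (power) | Detectable effect, restricted comparison |
|---|---|---|---|---|---|
| 1.0 | 0.31 | 0.30 (77%) | 0.65 (>99%) | 0.70 (>99%) | 0.31 |
| 0.8 | 0.39 | 0.24 (58%) | 0.52 (>99%) | 0.56 (>99%) | 0.32 |
| 0.6 | 0.52 | 0.18 (37%) | 0.39 (94%) | 0.42 (97%) | 0.32 |
| 0.5 | 0.62 | 0.15 (27%) | 0.325 (84%) | 0.35 (89%) | 0.33 |
| 0.4 | 0.78 | 0.12 (19%) | 0.26 (65%) | 0.28 (72%) | 0.34 |

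The 0.65 and 0.70 benchmarks fall below 0.31 only when p is under 0.31/0.65 = 0.48 and 0.31/0.70 = 0.44. The 0.30 benchmark is just under 0.31 before any dilution.

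**4. Where p might lie.** This is illustration only. Assume steady births, the Section 6 eligibility rule and recruitment in proportion to the eligible pool. Nine months of pregnancies plus six months of infants gives 9/15 = 0.60 pregnant at month-1 screening. Three months later, when counselling starts, (9 − 3)/15 = 0.40 of these women are still pregnant. Varying the registration delay from 0 to 3 months and the gap from 2 to 3 months gives 0.25 to 0.47 at the start. Recruitment favouring early pregnancy would raise this. Newly married women who are not yet pregnant would lower it at the start, and some of them may conceive during months 4 to 11.

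**5. Why restriction costs little.** With an ICC near 0.05 the number of centres dominates the variance, and all 20 are kept. At p = 0.4, m falls from 132 to 52.8, but the bracket rises only from 0.0475 + 0.9525/132 = 0.0547 to 0.0475 + 0.9525/52.8 = 0.0655.

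**The case against.** The stated group size is a ceiling, so a smaller group of pregnant women fits it. A reader might infer that the statements on group size and composition cannot all hold; the text does not go that far. It leaves open which assigned women are invited.

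A reader might also infer that most of the counselling arm would never be invited. No part of the protocol gives the pregnant share. The 0.40 above depends on uniform recruitment and a single start date, while Section 4 says the study targets women early in pregnancy and some before conception, and counselling runs for eight months.

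A third inference is that counsellors would apply different rules from village to village. Section 11 has a list supplied to the implementing partner, and Figure 1 schedules compliance checks, so this is speculation.

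Nor do the figures show that the trial is underpowered for every effect it cites: the two larger benchmarks stay above 0.31 SD at p = 0.6. The session topics (physical health, stress, relationships) could also serve women who have delivered; only the source sessions are described as pre-delivery.

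Finally, the analysis population is commonly left to the statistical analysis plan, which was not available here. If all assigned women are invited, or if the analysis is restricted by pregnancy status, the dilution does not arise.

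These objections limit the size and certainty of the problem. They do not settle who goes on the Section 11 list, or which women the 0.31 SD refers to. Both belong in the protocol.

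**Conclusion.** The point holds as a failure to reconcile. The Synopsis and Section 6 enrol women who are not pregnant, centre-level randomisation assigns them all to counselling or to no counselling, and the delivery description covers pregnant women only.

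The consequence is conditional. If assigned women who are not pregnant are not offered counselling, and all assigned women are analysed, the effect on the maternal primary outcomes is multiplied by p. The effect needed in women offered counselling rises from 0.31 SD to 0.39 at p = 0.8, 0.52 at 0.6 and 0.78 at 0.4. The benchmarks become 0.18, 0.39 and 0.42 SD at p = 0.6, or 0.12, 0.26 and 0.28 SD at p = 0.4. These values of p are assumptions, and it is not established that p is below one half. The calculation further assumes no effect in women not offered counselling, two-sided 0.05 and 80% power. It merits correction before allocation.

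**What to change.** Reconcile the Synopsis and Section 6 so that the list in Section 11 follows one invitation rule. Who should be offered counselling is for the investigators to settle. State the expected share of assigned women who meet the rule, and match the counselling comparison and its detectable effect to it.

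- **If all assigned women are to be invited,** bring the group description and the statement about pre-delivery sessions into line with that. The comparison over all assigned women and its 0.31 SD then need no adjustment on this account.
- **If groups stay limited to pregnant women,** define the counselling comparison in women recorded as pregnant in the administrative data at the month-3 allocation. Identify them identically in counselling and non-counselling centres, and keep the full sample as a supportive analysis. Section 6 says these data hold pregnancy status, and the status at month 3 precedes the start of counselling. Restate the detectable effect for this group: about 0.33 SD at p = 0.5 and 0.34 SD at p = 0.4, with p now the share pregnant at allocation and an ICC near 0.05.

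The cost is protocol wording and one field on the list. The second route loses a little precision and leaves out of the main comparison women who conceive after allocation and may join a group. It also keeps in any woman who delivers between allocation and her first session, so a little dilution could remain.
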